7.1. Study Subjects

7.1.1. Disposition of Subjects

Summaries of screened, consented and enrolled subjects will be provided overall, and in each arm (Abdominal and Thoracic) separately

Overall and for each indication, subjects in the Full Analysis Set (FAS), and in Per protocol Analysis Set (PPAS) will be summarized, according to follow-up, and within each investigational site.

Reason for study discontinuation will be tabulated based on FAS.

7.1.2. Clinical Investigation Plan (CIP) Deviations

Subjects with protocol deviations will be summarized and protocol deviations will be reported by type on overall FAS subjects and distinguishing minor and major protocol deviations/violations.

Major protocol deviations and violations will be defined and identified by the study team prior to run statistical analysis, based on protocol deviations listing provided by statistician.

7.1.3. Analysis Sets

SIGNIA Statistical Analysis Plan	
Version [Final#1.0] Page 12 of 15	Medtronic

Full Analysis Set (FAS): includes all enrolled and treated subjects (using Signia[™]). For this study, the Full analysis set corresponds to the safety population. FAS will serve as the primary analysis population for safety and performance analyses, as well as for demographics and baseline data analysis.

The per protocol Analysis Set (PPAS): includes all subjects from the FAS population who do not have a major protocol violation. Analyses on the PPAS will provide supporting evidence to the primary results (obtained on FAS).

7.2. General Methodology

Statistical analysis will be descriptive, and run separately in each arm:

- Continuous variables will be summarized using counts, means, standard deviations, medians, minimum and maximum.
- Categorical variables will be summarized using frequencies and percentages. Changes to the planned statistical analysis as defined in the protocol will be documented in the statistical analysis plan and clinical study report.

Some subgroup comparative analyses may be run in addition to primary and secondary endpoints, to assess impact of demographic characteristics, risk-factors, and surgery technique on the performance and safety outcomes.

In case of comparative analysis is performed:

- Pearson Chi-square test or Exact test will be used (as appropriate) for categorical data
- Student t-test or Wilcoxon rank sum test will be used if assumptions of t-test are not verified for continuous data.

7.3. Center Pooling

The study will be conducted in a minimum of 4 investigational sites. Screening and surgical data will be summarized for overall subjects and for each site separately, to confirm homogeneity of subject's characteristics between sites.

Primary and secondary endpoint analysis will be run on overall subjects. In case of imbalance regarding subject's characteristics between sites, additionnal subgroup analyses for primary and secondary endpoints could be performed according to investigational sites.

7.4. Handling of Missing, Unused, and Spurious Data and Dropouts

SIGNIA Statistical Analysis Plan	
Version [Final#1.0] Page 13 of 15	Medtronic

No data imputation will be performed for missing data. All practical monitoring and follow-up steps will be taken to ensure complete and accurate data collection.

Sample size has been determined including an attrition rate of 5% within 30 days for primary endpoint analysis.

7.5. Adjustments for Multiple Comparisons

Statistical analysis of primary endpoint is descriptive. No adjustment will be done.

7.6. Demographic and Other Baseline Characteristics

Screening and demographics characteristics, medical/surgical histories and risk-factors will be summarized using descriptive statistics.

7.7. Treatment Characteristics

For efficacy and safety endpoints assessment, some subgroup analyses may be run according to surgical technique and device caracteristics; all these characteristics may impact efficacy and safety results.

7.8. Interim Analyses

A preliminary analysis will be conducted in the study when 64 enrolled subjects complete the 30 day (+/-14days) follow up visit. The objective is to confirm early safety of the product. This interim analysis data review is driven by regional needs, to support a regulatory submission.

7.9. Evaluation of Objectives

Study objectives will be assessed through study endpoints measurement.

The primary endpoint is the incidence of subjects reporting serious adverse device effects up to and including 30 days (+14days) post-procedure which utilizes the Signia[™] Stapling System. It will be summarized using descriptive statistics.

A two-sided 95% confidence interval will also be calculated.

The analysis will be performed in abdominal group and in thoracic group, and in the combined groups, based on Full analysis Set, as defined previously. A confirmatory analysis of primary endpoint will be run using Per Protocol Analysis Set.

Secondary endpoints

SIGNIA Statistical Analysis Plan Medtronic Version [Final#1.0] Page 14 of 15

The secondary endpoint is device deficiency/malfunction affecting the intended performance of the device to include;

- Staple line assessment:
 - Intraoperative assessments:
 - Assessment of staple line integrity
 - Incidence of staple line bleeding (measured as \geq 50 cc)
 - Additional intervention(s) to treat staple-line failure (ex: glue, manual over sew, Medtronic buttress) or intraoperative revision/recreation of the anastomosis
 - Incidence of leakage (as measured by air leak test, or standard of care, as applicable)
 - Post-operative assessments:
 - Duration of air leakage (in days) for thoracic procedures
 - Prolonged air leaks are considered >7 days
 - Incidence of leakage for abdominal procedures as evidenced confirmed by imaging subject presentation or decline in status, or need for reoperation/re-intervention
 - Incidence of post-operative infection, assessed by the Investigator according to the standard of care and site policy, ex. positive wound culture
 - Additional intervention(s) to treat staple-line failure
- Incidence of repeat hospital admissions for primary procedure-related complications.

Secondary endpoints analysis will be run on Full Analysis Set and on Per-Protocol Analysis Set.

All recorded device deficiencies/malfunctions will be captured and assessed by the Investigator. Complaints will be handled in accordance with the standard procedures for the post-market vigilance system.

7.10.Safety Evaluation

Safety will be assessed as the proportion of subjects with AE based on the FAS, and on PPAS. AE incidence will be reported overall, and according to:

- Relation to the procedure
- Relation to the device including anticipated and unanticipated ADEs, related to:
 - Signia Stapling device, and/or
 - o Stapler reloads
- Severity,
- Seriousness.

Listing of AEs, SAEs, ADEs and SADEs, and UADEs will be provided based on FAS and PPAS, using the MEdDRA coding system classification for AE terms, and including characteristics described previously and AE outcome.

SIGNIA Statistical Analysis Plan Medtronic Version [Final#1.0] Page 15 of 15

7.11.Health Outcomes Analyses

Health outcomes analyses are already part of primary and secondary endpoints analyses, as described previously.

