4.1. Background

During abdominal and thoracic procedures, staple line failure can result in severe intraoperative and postoperative complications. After thoracic lung resection, postoperative air leaks are the most common complication with a reported occurrence between 4% and 58% [1-5]. In patients with concomitant chronic obstructive pulmonary disease (COPD) and fused fissures these rates can climb as high as 90% [6]. Thoracic air leak complications can include reduced mobility, increased hospital stay, the need for longer chest tube time (often associated with increased pain), and risk of further complications [1].

With the exception of staple lines across a distal obstruction or severe ileus, leaks are less common during gastrointestinal surgery due to lower intraluminal pressures to which the staple lines are exposed. If leaks do occur; however, the complications can be severe. Postoperative leak rates following laparoscopic sleeve gastrectomy (LSG) and laparoscopic Roux-en-Y gastric bypass (LRYGB) have been reported between 1% and 3% and leak-associated mortality has been reported at 0.1% [7-11].

[figure not shown]
Clearly, the integrity of the staple line is a primary factor in the creation of a stable anastomosis. The various characteristics of each tissue type present unique challenges and until now the firing speed used during these procedures was determined by the surgeon, particularly when using a manual firing setup [12]. Ultimately relying on generation of the ideal 'B' shaped staples, surgeon experience played a crucial role in effective staple line production [13, 12].

The Signia™ Stapling System with Endo GIA™ with Tri-Staple™ Technology and Tri-Staple™ 2.0 Intelligent Reloads uses a single-use reload. Automatically adjusting firing speed to optimize staple formation using an onboard intelligence, the Signia™ Stapling System generates consistent staple lines and real-time surgeon feedback via an OLED display. Additionally, the Signia™ Stapling System can be used single handed. To date single-handed use has proved challenging for many surgeons using manual firing systems.

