5.1.2. Secondary Objective(s)

The secondary endpoint is device deficiency/malfunction affecting the intended performance of the device to include;

MDT17025SIG Version 3.0 Page 19 of 57

- Staple line assessment:
 - o Intraoperative assessments:
 - Assessment of staple line integrity
 - Incidence of staple line bleeding (measured as ≥ 50 cc)
 - Additional intervention(s) to treat staple-line failure (ex: glue, manual over sew,
 Medtronic buttress) or intraoperative revision/recreation of the anastomosis
 - Incidence of leakage (as measured by air leak test, or standard of care, as applicable)
 - Post-operative assessments:
 - Duration of air leakage (in days) for thoracic procedures
 - Prolonged air leaks are considered >7 days
 - Incidence of leakage for abdominal procedures as evidenced confirmed by imaging subject presentation or decline in status, or need for reoperation/reintervention
 - Incidence of post-operative infection, assessed by the Investigator according to the standard of care and site policy, ex. positive wound culture
 - Additional intervention(s) to treat staple-line failure
- Incidence of repeat hospital admissions for primary procedure-related complications.

All recorded device deficiencies/malfunctions will be captured and assessed by the Investigator. Complaints will be handled in accordance with the standard procedures for the post-market vigilance system.

6. Study Design

The purpose of this study is to confirm the safety and performance of the Signia[™] Stapling System with Endo GIA[™] with Tri-Staple[™] Technology and Tri-Staple[™] 2.0 Intelligent Reloads in a minimum of 127 enrolled subjects undergoing indicated abdominal or thoracic procedures enrolled at approximately 10 sites in the USA and Europe (potentially in the United Kingdom, Spain, Italy).

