9.11. Subject Withdrawal or Discontinuation

9.11.1. Enrolled

A subject is considered enrolled in the study when it is confirmed they meet inclusion and exclusion criteria and ICF is signed and dated by subject and the Investigator and must be followed for the full 30 days if the procedure was begun or completed with the study device. Enrollment can take place 30 days before procedure and subjects will be followed for 30 (+14) days postoperative. If enrollment occurs greater than 30 days prior to procedure the subject will require to be reconsented.

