13.4.2. Secondary Endpoint

The incidence of secondary outcome measures will be summarized using descriptive statistics:

- counts and percentages for categorical data
- mean, standard deviation, median, minimum and maximum for quantitative data.

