13.5. Handling of Missing Data

No data imputation will be performed for missing data unless otherwise noted in statistical analysis plan. All practical monitoring and follow-up steps will be taken to ensure complete and accurate data collection.

Sample size has been determined including an attrition rate of 5% within 30 days for primary endpoint analysis.

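### The SAP has no rule for a thoracic air leak still open at last contact, so its plain summary of leak duration is biased low by an unknown amount

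*SAP*

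**What the plan says.** Protocol 5.1.2 and SAP 4.2 and 7.9 list "Duration of air leakage (in days) for thoracic procedures" among the post-operative secondary assessments, with the cut-off "Prolonged air leaks are considered >7 days".

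The method is purely descriptive. Protocol 13.4.2 gives "mean, standard deviation, median, minimum and maximum for quantitative data". SAP 7.2 says the same: "Continuous variables will be summarized using counts, means, standard deviations, medians, minimum and maximum".

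On missing data, Protocol 13.5 leaves an opening: "No data imputation will be performed for missing data unless otherwise noted in statistical analysis plan". SAP 7.4 does not use it: "No data imputation will be performed for missing data".

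Follow-up is finite. Protocol 9.11.1 states that "subjects will be followed for 30 (+14) days postoperative". Protocol 13.5 and SAP 7.4 allow for 5% attrition within 30 days, and Protocol 9.11.4 and 9.11.5 provide for withdrawal and loss to follow-up. Protocol 11.1.9 has an adverse-event outcome category for events continuing at study end, but nothing connects it to the duration endpoint.

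Neither document gives a censoring rule, a time-to-event summary or a minimum-duration rule. Neither says whether the 7-day flag is derived from a completed duration.

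**The concern.** A duration needs a start and an end. A leak still present when the subject is last seen has only a lower bound. With ordinary summary statistics and no imputation, one of two things happens by default: the duration is missing and leaves the summary, or the site enters the time to last contact as if the leak had closed then.

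Both errors point the same way. The longer a leak lasts, the more likely it is to be open at last contact, so the affected durations come mainly from the long end. The mean and maximum look shorter than they are, the median moves less, and the staple line appears to perform better. As the plan does not ask for the number of open leaks beside the duration summary, a reader of the results could not tell whether the effect is trivial or not.

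**Working it through.** **No figure to reproduce for this endpoint.** The documents give no expected duration and no expected number of open leaks. The planning figure for the same arm does reproduce: Poisson mean 74 × 0.95 × 0.025 = 1.7575, so P(at least 1) = 1 − e^(−1.7575) = 82.8%, against the stated 83%. That confirms the 74 subjects and 5% attrition used below, but says nothing about leak duration.

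**How many leaks.** Protocol 4.1 gives a "reported occurrence between 4% and 58" per cent. Applied to 74 subjects: 74 × 0.04 = 3.0 and 74 × 0.58 = 42.9, so about 3 to 43 leaks.

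**Small-number illustration (assumed: closed leaks average 4 days, open leaks last seen at Day 30).** With L leaks, u of them open, the mean is at least ((L − u) × 4 + u × 30)/L.

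- L = 15, u = 1: (14 × 4 + 30)/15 = 5.7 days. Leaving the open leak out reports 4.0. Entering it at 30 days reports 5.7, which is only the lower bound.
- L = 43, u = 1: (42 × 4 + 30)/43 = 4.6 days, against 4.0.

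**Distributional range (assumed lognormal, median m of 3 or 5 days, log-SD s of 0.8 or 1.2).** The true mean is M = m × e^(s²/2). With everyone seen to Day 30, let A = Φ((ln 30 − ln m)/s) and B = Φ((ln 30 − ln m − s²)/s). The share open is 1 − A. The mean of closed leaks is M × B/A. The mean with open leaks entered at 30 days is M × B + 30 × (1 − A).

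| Case | M | A | B | Open leaks left out | Open leaks entered at 30 days |
|---|---|---|---|---|---|
| m = 3, s = 0.8 | 4.13 | 0.9980 | 0.9812 | 4.06 | 4.11 |
| m = 5, s = 1.2 | 10.27 | 0.9323 | 0.6153 | 6.78 | 8.35 |

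Adding 5% lost uniformly over Days 0 to 30 (simulation, 1,000,000 draws per case), over all four combinations of m and s:

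- 0.9% to 7.8% of leaks are open at last contact.
- Leaving them out takes the mean from 4.13 to 4.04 days in the mildest case and from 10.25 to 6.70 in the heaviest-tailed. (The simulated true mean of 10.25 is the 10.27 above, within simulation error.)
- The median falls by 0.02 to 0.53 days.

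**Prolonged leaks, same simulation.** If the flag needs a closed duration, the share over 7 days goes from 14.4% to 14.1% (mildest) or from 38.9% to 34.1% (heaviest-tailed). If a leak seen open after Day 7 is counted as prolonged without an end date, the shares are 14.3% and 38.7%, within about 0.2 points of the truth.

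**The case against.** The strongest reply is that the documents are silent and do not prescribe exclusion. No section says that an open leak is dropped, and the case report form, which would show how duration is captured, is not among the documents. That stands: exclusion is a default consequence, not a stated rule. The alternative, entering the time to last contact, still understates the duration.

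Several provisions limit the problem:

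- Treated subjects must be followed for the full 30 days (Protocol 8.2, 9.11.1).
- Air leak is a named example of an adverse device effect (Protocol 9.7.2), and events judged device-related are followed to resolution where possible (Protocol 11.2).
- Adverse-event outcome is recorded (Protocol 11.1.9) and listed (SAP 7.10), so an open leak reported as an event would be visible.

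This is real but partial mitigation. Extended follow-up applies only to leaks judged device-related, and Protocol 11.1.8 treats complications of procedures that would have been done anyway as unrelated.

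The median is already planned and is fairly robust. That also stands; the mean and maximum are the exposed statistics.

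Finally, Kaplan-Meier adds little precision when leaks are few, and censoring at death or at a loss linked to the leak is open to question. Both are fair, and are reasons to report the number censored beside the estimate.

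**Conclusion.** The gap is real and its direction is known. A plain summary with no imputation and no rule for open leaks biases mean and maximum duration low, and the median less. The size is not determinable from the documents. With follow-up to Day 30 it runs from negligible (4.13 to 4.04 days) to large (10.25 to 6.70), and this range rests on assumed lognormal durations and assumed uniform loss.

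Three stronger readings are tempting and not supported:

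- **That prolonged leaks are necessarily undercounted.** A leak seen open after Day 7 is already known to exceed 7 days, and nothing in the plan requires an end date before it is counted. The count is low only if the flag is programmed from a closed duration, or if contact ends on or before Day 7.
- **That several open leaks should be expected.** Two open out of 15 is 13%, above the 0.9% to 7.8% in the Day 30 scenarios, which correspond to 15 × 0.009 = 0.1 to 15 × 0.078 = 1.2 leaks.
- **That the mean could fall by 32% to 71%.** That result needs leak status to be last seen at discharge (assumed uniform on Days 3 to 10). The schedule places the staple line assessment on Day 0 only, but adverse events and device effects are collected again at the Day 30 visit.

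The endpoint is secondary and descriptive, with no acceptance criterion. The primary endpoint and sample size are unaffected, and this is a minor improvement.

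**What to change.** Add to SAP 7.9:

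1. Count as prolonged every leak documented as present after Day 7, whether or not its end date is known.
2. Among thoracic subjects with a leak, treat a leak without an observed end as right-censored at the last date it was known to be present. Report the Kaplan-Meier median with the number censored.
3. Report the number of leaks still open at discharge and at study exit. If a simple mean is kept, label it as covering resolved leaks only.

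The cost is SAP wording and minor extra programming, with no added subjects or procedures, provided that the case report form dates the last observation of a leak. That should be checked first, because the documents do not show the form. The reported duration may be less favourable, and the Kaplan-Meier estimate will be imprecise if leaks are near the lower end of the 3 to 43 range.

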9.1. Schedule of Events

9.1.1. Study schematic

Procedure/Assessment	Screening (Day -30 to 0)	Operative (Day 0)	Discharge	Follow-up Assessment
Procedure/Assessment	Can be combined		Assessment	(at 30 Days (+14 days))
Informed Consent ¹	X			
Eligibility Criteria	Х	X		
Pregnancy check via urine or serum pregnancy test females of child bearing potential (USA only) or per EU local requirements	X ²	X ²		
Demographic Data	X			
Vital Signs	X	X		
BMI	X			
Abbreviated Physical exam ³	X	X		
Medical and surgical history, including previous abdominal or thoracic surgical history	Х			
American Society of Anesthesiologists (ASA) grade		Х		
Operative date		X		
Operative start/stop times		X		
Type of procedure		X		
Anesthesia details		X		
Study device data ⁴		X		
Use of feedback display (if applicable)		X		
Concomitant medications ⁵		X	X	X
Procedure Related Adverse Events		X	X	X
Adverse Device Effects (ADEs)		X	X	X
Staple line assessment		X		
Device deficiencies/ malfunctions ⁶		X		
Device Accountability		X		
Length of hospital stay			X	
Length of intensive care stay (if applicable)			X	
Surgical site and infection assessment by the				
Investigator according to the standard of care and site policy, ex. Positive wound culture			Х	Х
Readmission- related to primary procedure				Х
No study procedures will be performed until informed.	consent form has been	n completed Subjects	should he re-consent	

^{1.} No study procedures will be performed until informed consent form has been completed. Subject should be re-consented if date of original consent is greater than 30 days.

MDT17025SIG Version 3.0 Page 30 of 57

Procedure/Assessment	Screening (Day -30 to 0)	Operative (Day 0)	Discharge	Follow-up Assessment
	Can be o	combined	Assessment	(at 30 Days (+14 days))

- 2. If Screening and Surgery occur on different days, these procedures should occur during Screening and be reconfirmed on the day of surgery.
- 3. Including height, weight, and examination of the heart, lung, and abdomen as applicable
- 4. Including but not limited to, staple size, number of firings, type of reload used, location of firings, lot number of devices used, malfunctions
- 5. Only those related to relevant medical history or adverse events will be collected, e.g.: anticoagulants, blood pressure, antibiotics, pain medications
- 6. Including but not limited to system set-up (insertion guide, power shell), OLED screen display, rotation, articulation, clamp/unclamp, firing, use of manual retraction tool

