11.1. Definitions/Classifications

11.1.1. Adverse Event (AE)

In alignment with ISO 14155:2011 (Section 3.2), an Adverse Event is any untoward medical occurrence, unintended disease or injury, or untoward clinical signs (including abnormal laboratory findings) in subjects, users or other persons, whether or not related to the investigational medical device.

This definition includes events related to the study device and the procedures involved. For users or other persons, this definition is restricted to events related to study devices.

For study purposes, the following occurrences are considered to be expected observations following surgical procedures (primarily associated with anesthesia) and will not be considered reportable AEs, as long as the event is not associated with significant sequelae, does not prolong hospitalization, and responds to standard medical therapy:

- Postoperative transient nausea determined to be procedure related within the first 24 postoperative hours.
- Postoperative transient emesis determined to be procedure related within the first 24 postoperative hours.
- Postoperative constipation, determined to be procedure and/or medication related for the duration of medication administration for management of pain.
- Postop pain that the Investigator considers common and within normal limits for the procedure and is well-managed with medication.

For study purposes procedure related adverse events will be collected and documented at the time of the procedure and up to and including the 30 day (+14 days) post-operative follow up visit.

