11.1.2. Serious Adverse Events (SAE)

In alignment with ISO 14155:2011 (Section 3.37), a serious adverse event (SAE) is any AE that has:

- led to death,
- led to serious deterioration in the health of the subject that either resulted in
 - o a life-threatening illness or injury, or
 - o a permanent impairment of a body structure or a body function, or
 - in-patient or prolonged hospitalization, or
 - medical or surgical intervention to prevent life threatening illness or injury or permanent impairment to a body structure or a body function, or
- led to fetal distress, fetal death, or a congenital abnormality or birth defect.

MDT17025SIG Version 3.0 Page 39 of 57

NOTE: Planned hospitalization for a pre-existing condition or a procedure required by the clinical investigational plan, without serious deterioration in health, is not considered an SAE.

SAEs will be collected and documented at procedure and up to and including the 30 day (+14 day) post-operative follow-up visit.

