11.1.8. Adverse Event Relationship Classification

Causality assessments define the relationship between the use of the medical device (including the medical-surgical procedure) and the occurrence of each adverse event, according to MEDDEV (Guidelines on Medical Devices, Clinical Investigations: Serious Adverse Event Reporting). The presence of confounding factors, such as concomitant medication/treatment, the natural history of the underlying disease, other concurrent illness or risk factors shall also be considered.

Each AE will be classified according to five different levels of causality. The sponsor and the investigators will use the following definitions to assess the relationship of the serious adverse event to the investigational medical device or procedures:

MDT17025SIG Version 3.0 Page 41 of 57

Not related: relationship to the device or procedures can be excluded when:

- 1. the event is not a known side effect of the product category the device belongs to or of similar devices and procedures
- 2. the event has no temporal relationship with the use of the device or the procedures;
- 3. the serious event does not follow a known response pattern to the medical device (if the response pattern is previously known) and is biologically implausible;
- 4. the discontinuation of medical device application or the reduction of the level of activation/exposure when clinically feasible and reintroduction of its use (or increase of the level of activation/exposure), do not impact on the serious event;
- 5. the event involves a body-site or an organ not expected to be affected by the device or procedure;
- 6. the serious event can be attributed to another cause (e.g. an underlying or concurrent illness/clinical condition, an effect of another device, drug, treatment or other risk factors);
- 7. the event does not depend on a false result given by the device used for diagnosis, when applicable;
- 8. harms to the subject are not clearly due to use error;
- 9. In order to establish the non-relatedness, not all the criteria listed above might be met at the same time, depending on the type of device/procedures and the serious event.

Unlikely: the relationship with the use of the device seems not relevant and/or the event can be reasonably explained by another cause, but additional information may be obtained.

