Assessment of the occurrence of an AE will be based on changes in the subject's abbreviated physical examination, laboratory results and/or signs and symptoms. Adverse events will be monitored until a subject completes the study unless the Investigator determines the event is related to the device, in which case they will be monitored until resolution if possible. Medical care will be provided, as defined in the informed consent, for any AE related to study participation. Adverse events will be collected on an AE eCRF and applicable source documentation. To the extent possible, the event to be recorded and reported is the event diagnosis as opposed to event symptoms (e.g., fever, chills, nausea and vomiting in the presence of a clinically diagnosed infection is to be reported as infection only). For the purposes of this protocol, only those AEs occurring after enrollment will be recorded.

The following should not be considered an AE:

- A condition requiring a preplanned procedure unless the condition worsened since screening
- A preexisting condition found as a result of screening, unless the condition has worsened since enrollment

All responses to the above events that require treatment beyond the institution's standard procedures will be reported as AEs.

All device and procedure related AEs observed during the course of this study (up to and including the 30day follow up visit), regardless of severity or relationship to the device will be recorded on the appropriate eCRF.

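### SAP 7.10 reports an overall AE incidence, but the collection instructions cover only procedure-related AEs, ADEs and SAEs

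*SAP*

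**What the plan says.** SAP 7.10 sets the safety measure: "Safety will be assessed as the proportion of subjects with AE based on the FAS, and on PPAS". It adds that "AE incidence will be reported overall, and according to" relation to the procedure, relation to the device (stapler and/or reloads), severity and seriousness. Nothing there limits the AEs to related ones.

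The instructions that tell sites what to record are narrower:

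- Protocol 11.1.1: "For study purposes procedure related adverse events will be collected and documented at the time of the procedure", and on through the Day 30 (+14) visit.
- Protocol 11.2, closing paragraph: the subject of the sentence is "All device and procedure related AEs observed during the course of this study", and these, "regardless of severity or relationship to the device will be recorded on the appropriate eCRF".
- The schedules in protocol 9.1.1 and SAP section 5: the only AE rows are "Procedure Related Adverse Events" and ADEs. The visit lists in protocol 9.7.1 to 9.7.3 name the same two categories.
- Protocol 11.1.2: "SAEs will be collected and documented at procedure and up to and including the 30 day (+14 day) post-operative follow-up visit", with no relatedness condition.

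Other wording is broader. Protocol 9.8 lists AEs, without a relatedness limit, among the events monitored and entered in the eCRF. Protocol 11.1.8 says "Each AE will be classified according to five different levels of causality", and the lowest level is not related. An earlier paragraph of 11.2 sends adverse events to an AE eCRF, and the limit it gives is that they occur after enrolment.

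**The concern.** Under the narrow instructions, relatedness is both an attribute that SAP 7.10 tabulates and the condition for a non-serious event to enter the dataset. Serious events face no such condition. A table headed overall AE incidence would be read as the share of subjects with any AE, and it would not be that.

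The study exists to confirm safety, its results are meant for publication, and the interim look supports a regulatory submission, so the label will be taken at face value. Because the protocol also contains broader wording, sites may apply different rules, and the pooled figure could then mix two definitions.

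**Working it through.** **Step 1. Which events have a recording instruction?**

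- Non-serious, procedure-related: yes (11.1.1, 11.2, schedules, visit lists).
- Non-serious, device-related: yes, as ADEs (11.1.3, 11.2, schedules, visit lists).
- Serious, any relationship: yes (11.1.2).
- Non-serious, unrelated to both procedure and device: none in those sections. Only the general wording of 9.8, 11.1.8 and 11.2 could bring these in.

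Protocol 11.1.1 also removes listed expected observations, such as transient nausea, under stated conditions. The collection sections do not say which of the five causality levels counts as procedure-related.

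**Step 2. What do the SAP 7.10 outputs become?**

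- Overall: subjects with a procedure-related AE, an ADE or an SAE.
- Relation to procedure: any unrelated category would hold SAEs, plus any non-serious ADE judged not procedure-related, so almost only serious events.
- Relation to device: any unrelated category would hold procedure-related events and SAEs, but no other non-serious events.
- Severity, and the non-serious side of seriousness: collected events only.

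**Step 3. What stays intact?** Device-related AEs, procedure-related AEs and SAEs are each collected by instruction, and the Full Analysis Set (FAS) denominator does not depend on AE collection. Their incidences are unaffected. A serious ADE is both serious and device-related, so the primary endpoint is also unaffected.

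**Step 4. How large could the shortfall be?** The plan states no AE incidence to reproduce and gives no rate for unrelated non-serious AEs. The following is an illustration only. Let r be the proportion of subjects with a collected event and u the proportion with at least one uncollected event, assumed independent.

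- True any-AE incidence = 1 − (1 − r)(1 − u)
- Shortfall = u(1 − r)

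With assumed ranges r = 10 to 40% and u = 5 to 30%, and 127 subjects all treated:

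- Smallest: 0.05 × (1 − 0.40) = 0.03, or 3 points; 127 × 0.03 = 3.8 subjects.
- Largest: 0.30 × (1 − 0.10) = 0.27, or 27 points; 127 × 0.27 = 34.3 subjects.

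Overlap matters. If every subject with an uncollected event also has a collected one, the shortfall is 0. If none does, it is u itself, up to 30 points here.

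**The case against.** The strongest reply is that the documents do not state a clean filter. A reader might infer that unrelated non-serious AEs are never recorded. Protocol 9.8, 11.1.8 and the AE eCRF paragraph of 11.2 prevent that conclusion: the text is inconsistent, and some sites may record such events. This part of the reply stands. It does not rescue the SAP label, because none of that wording gives sites a visit-level instruction to collect them.

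Three further inferences are tempting and not supported.

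- **That the serious share of AEs is inflated.** SAP 7.10 plans proportions of subjects in the analysis sets, not a ratio of serious to all AEs. The SAE incidence has the same numerator and denominator either way.
- **That 11.2 contradicts itself and the phrase about relationship to the device should go.** It has an ordinary reading: procedure-related AEs are recorded whatever their severity or relation to the device. Deleting it would remove the words that keep procedure-related events not attributed to the device.
- **That missed events defeat independent review.** Protocol 12.2 has the Independent Medical Monitor adjudicate prespecified events supporting the endpoints and review SAEs; it promises no re-rating of every non-serious AE. Staple-line bleeding of at least 50 cc, leakage and infection are also separate secondary outcomes with no relatedness condition.

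It can also be said that restricted collection is a legitimate choice in a descriptive post-market study. That stands, and it is why collecting every AE is optional.

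**Conclusion.** The point holds as a mismatch between a stated safety output and the instructions that feed it. Followed as written, those instructions produce an overall AE incidence covering procedure-related AEs, ADEs and SAEs only, and it understates any-AE incidence. The documents do not allow the amount to be derived. The 3 to 27 points rest on assumed rates and independence, and show only that the gap need not be trivial.

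The defect is confined to the overall figure, the rows that inherit its restriction, and any related-versus-unrelated comparison. The acceptance criterion for the primary endpoint is not touched. It is worth correcting before analysis because the correction is nearly free.

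**What to change.** In SAP 7.10:

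- Replace the overall AE incidence with the proportion of subjects with procedure- and/or device-related AEs, and add a separate table of all SAEs.
- State that non-serious AEs unrelated to both procedure and device are not systematically collected.
- Draw no any-AE incidence and no related-versus-unrelated share from these data.

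In the protocol, align 9.8, 11.1.1, 11.1.8 and 11.2 to one collection rule. In 11.2, clarify the phrase instead of deleting it, so that it plainly says procedure-related AEs are recorded whatever their severity or relation to the device.

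The cost is wording in two documents and the loss of an any-AE headline figure. If the sponsor wants that figure, the optional alternative is to record all AEs regardless of relationship at the visits already scheduled and rate relatedness afterwards. That adds AE forms and is not required to resolve the point.
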